7.6.3.2. Cuff Placement and Measurement

Masimo INVSENSOR00073 cuff shall be placed on the opposite limb from the arterial line. Care should be taken to ensure that both the arterial line transducer and Masimo INVSENSOR00073 cuff are at the level of the participant's left ventricle of the heart. Data collection software(s) will be set up for data acquisition.

[figure not shown]
7.6.3.3. Blood Pressure Variations Procedure

During the blood pressure variations procedure, participants will be administered continuous infusions containing vasoactive medications. There will be two study types:

[figure not shown]
[figure not shown]
Induced controlled hypertension (increased blood pressure)

Induced controlled hypotension (decreased blood pressure)

Both study types will involve the use of a primary drug to elicit the desired blood pressure change.

Vasoactive Medication

[figure not shown]
[figure not shown]
 will be used as the primary drug to induce hypertension (increased blood pressure) and  will be used to induce hypotension (decreased blood pressure).

Study Title: Validation Study of Mean Arterial Pressure (MAP) Parameter of Masimo
INVSENSOR00073

Revision: 

Safety drugs will be used to counteract the effects of the primary drugs when deemed necessary by the presiding clinician. Table 1 outlines the possible primary and safety drug choices based on the pressure variation study type.

Table 1. Drugs allowed for pharmacological variations of blood pressure variation studies.

Type of Pressure Variation Study	Primary Drug	Safety Drug
		
		

Blood Pressure Safety Limits

Medication-induced blood pressure variation studies have strict pressure variation limits to ensure the subject's blood pressure stays within a safe range. Tables 2 and 3 below outline the maximum allowable pressure variations for each study type. If the blood pressure limits are reached or exceeded, drug infusion will be stopped immediately, and the subject will be monitored as blood pressure returns to the baseline values. The study may be continued if the subject is comfortable, and clinicians deem it is safe to proceed.

Target blood pressure changes must be determined prior to starting the study for each subject. The selected variation must be the lesser of the percent and absolute changes indicated in Table 2, provided the selected variation does not violate the limits established in Table 3. Vasoactive medications are titrated based upon the arterial line-derived mean arterial pressure (MAP) reading. Blood pressures must remain within the limits defined in Table 3 for the duration of the procedure.

Table 2. Maximum allowed pressure variations for each study type. Target pressure variations are calculated based on mean arterial pressure (MAP)

Study Type	Percent Change From Baseline MAP	Absolute Change From Baseline MAP
Controlled Hypertension		
Controlled Hypotension		

Table 3. Minimum and Maximum blood pressure levels

[figure not shown]
Blood Pressure	Minimum (mmHg)	Maximum (mmHg)
Systolic Blood Pressure		
Diastolic Blood Pressure		

Study Title: Validation Study of Mean Arterial Pressure (MAP) Parameter of Masimo
INVSENSOR00073

Revision: 

Mean Arterial Pressure (MAP)  

[figure not shown]
Medication Preparation and Administration

Primary and safety drugs will be prepared for each subject prior to beginning the blood pressure variation procedures. A trained clinician will prepare all infusions containing the primary drug. 

[figure not shown]
Only full and unused syringes will be used for each subject. Partially used syringes will be discarded after each subject completes the study.

Infusion rates for each titration step are calculated by the medication infusion pump based on the subject's weight  and the drug concentration. 

 Two independent clinicians must verify medication pump settings before changing the current setting.

If the subject participates in the induced hypertension procedure (increased blood pressure), the infusion with  will be given at a starting dose of  µg/kg/min. 

If the subject participates in the induced hypotension procedure (decreased blood pressure), the infusion with  will be given at a starting dose of  µg/kg/min. 

After gauging subject response to the initial infusion, the drug will be titrated to achieve the desired blood pressure variation. Dose increases may continue to titrate up to the targeted blood pressure change as long as the subject remains 

[figure not shown]
Study Title: Validation Study of Mean Arterial Pressure (MAP) Parameter of Masimo
INVSENSOR00073

Revision: 

asymptomatic and the dose does not exceed the maximum of  µg/kg/min. See Table 4 for the  and  dose schedules.

Table 4. Dose schedule for  and 

Drug	Starting Dose (µg/kg/min)	Step Size/Schedule (µg/kg/min)	Maximum Dose (µg/kg/min)	Dose Increase Wait Time
				
				

Primary drug infusion stops when the target blood pressure change is maintained for the period of time  the subject develops symptoms, blood pressure limits are reached/exceeded, or the total drug infusion time per  After primary drug infusion ceases, the subject's blood pressure is allowed to passively return to baseline. Baseline is considered achieved when the subject's blood pressure is within 10 mmHg of their initial blood pressure levels.

The total drug infusion time (including all Rounds) must not exceed 180 minutes. If this limit is reached, the blood pressure variation procedures will be stopped.

Post-administration monitoring may exceed 60 minutes.

7.6.3.4. Safety Drug Administration Procedure

Safety Drugs will be prepared for administration prior to beginning the blood pressure variation procedures. Weight-appropriate doses will be chosen for each subject and verified by a clinician. If the presiding clinician deems it necessary to begin safety drug administration, the primary drug infusion will be stopped immediately and the clamp on the vasoactive drug line closed. The safety drug will be administered at the  Clinicians will monitor the subject's response to the safety drug, repeating the reversal as necessary and at the presiding clinician's discretion to facilitate the subject's return to baseline blood pressure.

7.6.3.5. Ending Procedures

At the conclusion of the procedure, the sensors/devices, IVs, and arterial lines will be removed. A set of pre-discharge vitals, such as heart rate and blood pressure, will be obtained and recorded on the case report form for subject safety purposes.

Subjects will not be allowed to leave until blood pressure has returned within 10 mmHg of baseline blood pressure values, they have been asymptomatic for a minimum of 5 minutes, and medical personnel determine it is safe to do so.

Subjects will be offered a snack (e.g., granola bar) and something to drink (e.g., water or juice). Subjects may be asked to consume food and/or liquid prior to leaving the clinical lab area for their safety due to study procedures such as line placement and blood removal.

Subjects will be encouraged to remain in the study area until they feel fit to leave. Subjects should feel safe and able before returning to work directly after participation in the study and will be advised to take as much time as they need after the study before returning to work.

Subjects will be given instructions on post care. All subjects will be instructed to contact the principal investigator or study staff in the event of any potential complication.

The total overall lab time will be approximately 180 minutes. If the total lab time exceeds 180 minutes, subjects will be compensated for the additional time. Subjects will be paid according to the compensation breakdown on the consent form.

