While a blood pressure variation procedure is not free of risks, risks have been mitigated. Potential hazards associated with use of [REDACTED] and [REDACTED] include overdose and overreaction to the drug. There is also a possibility of cyanide poisoning, though highly unlikely. Accordingly, subjects will start at [REDACTED] $\frac{\mu\text{g}/\text{kg}}{\text{min}}$ of [REDACTED] and [REDACTED]. An increase of dose will only occur if the subject is asymptomatic. Safety drugs as outlined in Table 2 (see section 7) will also be used should it be deemed necessary by the presiding clinician. The infusion will be stopped through safety clamp or stopcock immediately, should continuation with the procedure be deemed unsafe for the participant.

Similarly, an invasive A-line placement for blood pressure measurements is not free of risks; accordingly, to mitigate risks, participants are monitored by study staff (including an Advanced Cardiovascular Life Support (ACLS)-certified physician) for the duration of blood pressure variation procedure, provided with post care instructions discharge, and can reach Masimo in the case of any complications after discharge.

Once the blood pressure variation procedure has been completed, the subject will be monitored until their pressure is within 10 mmHg of their baseline and they have been asymptomatic for approximately 30 minutes.

Other requirements of *ISO 81060-2* pertain to sex and cuff size distributions (detailed in section 8 below). Accordingly, a targeted enrollment approach will be used to select participants across the spectrum needed for the validation study.

5. BENEFITS AND RISKS OF THE INVESTIGATIONAL DEVICE, CLINICAL PROCEDURE, AND CLINICAL INVESTIGATION

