Subjects will be monitored closely for onset of symptoms while inducing controlled hypotension using vasoactive medications. These typically resolve quickly when blood pressure returns to baseline once infusion has stopped. Sodium thiosulfate and sodium nitrite will be present to counter potential cyanide poisoning from [REDACTED]. The safety drug to reverse the effects of [REDACTED] is [REDACTED] and it will be administered at the discretion of a trained clinician.

- Risks Associated with [REDACTED]

[REDACTED] is included for situations calling for inotropic support in addition to the vasoconstrictor. [REDACTED] is used in this protocol as a safety drug for [REDACTED].

Risks include but are not limited to tachycardia, hypertension, headache, anxiety, apprehension, palpitations, diaphoresis, nausea, vomiting, weakness, and tremors. These typically resolve quickly when blood pressure returns to baseline once infusion has stopped.

- Risks Associated with Accidental Exposure to Bloodborne Pathogens

While care is taken to ensure that blood samples are handled safely, and though unlikely, there is a possibility that study personnel could become exposed to bloodborne pathogens through accidental or occupational exposure to blood samples from subjects who carry bloodborne pathogens, such as Hepatitis B Virus (HBV), Hepatitis C Virus (HCV), or Human Immunodeficiency Virus (HIV). In such circumstances, study participants could also be at risk and past study participants will be contacted regarding additional testing to be done at an outside facility (e.g., outside laboratory, urgent care clinic, etc.). Subjects will only be compensated for the cost of exposure determination testing and their time/travel accommodation to the testing facility.

- Risks from Inflicted Knowledge

In the case that a subject becomes aware of a condition (arrhythmia, etc.) during the study, our study staff will recommend that they contact their primary care physician, and we will document this recommendation.

- Risks from Loss of Confidentiality

Masimo upholds the highest standards to protect hard and electronic data, however, a complete promise for confidentiality cannot be guaranteed due to unforeseeable events.

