11. DEVIATIONS FROM CLINICAL INVESTIGATION PLAN

Deviations from the protocol must receive both sponsor and the investigator's IRB/ethics committee approval before they are initiated, with the exception that under emergency circumstances, deviations from the *Clinical Investigation Plan* to protect the rights, safety and well-being of human subjects may proceed without prior approval of the sponsor or the IRB/ethics committee.

Any protocol deviations initiated without sponsor and the investigator's IRB/ethics committee approval that may affect the scientific soundness of the study, or affect the rights, safety, or welfare of study subjects, must be documented and reported to the sponsor and to the investigator's IRB/ethics committee as soon as a possible, but no later than 5 working days after the occurrence of the protocol deviation. In addition to documenting deviations on the CRF, the *Protocol Deviation Form* may also be used. If protocol deviations continue to occur frequently at a study site, a corrective and preventive action (CAPA) may be opened by the sponsor.

Withdrawal of IRB approval: An investigator shall report to the sponsor a withdrawal of approval by the investigator's reviewing IRB as soon as possible, but no later than five working days of the IRB notification of withdrawal of approval.

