13. STATEMENTS OF COMPLIANCE

This document is a clinical investigational plan for a human research study sponsored by Masimo Corporation. The study will be conducted in accordance with the ethical principles that have their origin in the Declaration of Helsinki.

By participating in the study, the Investigator agrees to adhere to all stipulations of this protocol, the conditions of the IRB or Research Ethics Committee approval, federal and local regulatory requirements, 21 CFR 812, ISO-14155, ICH GCP guidance.

The protocol, ICFs, recruitment materials, and all subject materials will be submitted to the IRB for review and approval. Approval of both the protocol and the consent form must be obtained before any subject is enrolled. Any amendment to the protocol will require review and approval by the IRB before the changes are implemented to the study.

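### Section 4 promises monitoring until volunteers have been symptom-free for about 30 minutes, but the discharge rule in Section 7.6.3.5 asks for only 5, and no readable text reconciles the two.

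*Combined protocol and SAP*

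**What the plan says.** Section 4 (Justification for Clinical Investigation Design Plan) describes how the risks of the infusions and the arterial line are reduced. It then states that, after the blood pressure variation procedure, "the subject will be monitored until their pressure is within 10 mmHg of their baseline and they have been asymptomatic for approximately 30 minutes".

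Section 7.6.3.5 (Ending Procedures) is where the conditions for leaving are set. Pressure must be back within 10 mmHg of baseline, and volunteers must stay until "they have been asymptomatic for a minimum of 5 minutes, and medical personnel determine it is safe to do so".

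Two other statements bear on the period after infusion, both in Section 7.6.3.3. Baseline counts as regained when "blood pressure is within 10 mmHg of their initial blood pressure levels". The section also notes: "Post-administration monitoring may exceed 60 minutes".

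**The concern.** The pressure condition is the same wherever it appears; the symptom-free time is not. Section 4 offers the longer period as a safeguard for people who get no direct benefit from taking part (Section 5.1). The listed drug risks in Section 5.2.2 include fainting, confusion, blurred vision, hypotension and cyanide poisoning. By discharge the lines have been removed, so observation is one of the remaining protections.

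There is also a compliance problem. Under Section 13, "the Investigator agrees to adhere to all stipulations of this protocol". A release at, say, 10 symptom-free minutes with medical clearance satisfies Section 7.6.3.5 and still departs from Section 4. If such an unapproved departure may affect safety, Section 11 requires it to be reported "no later than 5 working days after the occurrence of the protocol deviation". Nothing in Section 7.6.3.5 would tell staff that a departure had occurred.

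**Working it through.** This is a comparison of texts. The plan gives no figure to reproduce, and no sample size, power or error rate is involved.

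**The provisions side by side**

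| Place | Pressure condition | Symptom-free time | Other condition |
|---|---|---|---|
| Section 4 | within 10 mmHg of baseline | about 30 minutes | none stated |
| Section 7.6.3.3, return to baseline | within 10 mmHg of initial levels | none stated | none stated |
| Section 7.6.3.3, monitoring after infusion | none stated | none stated | may run past 60 minutes; no minimum |
| Section 7.6.3.5 | within 10 mmHg of baseline | at least 5 minutes | medical staff judge it safe |

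**Can the two periods be reconciled?**

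1. *Meeting both.* A volunteer who waits 30 symptom-free minutes satisfies both rules, so they are not logically exclusive. But a volunteer who has been symptom-free for between 5 and 30 minutes passes one rule and fails the other.
2. *Two stages.* The 30 minutes could follow the infusion and the 5 minutes could be a final check after line removal. Section 7.6.3.5 does not start its 5 minutes at line removal. It also still lists recovery of pressure as a condition to be met, which would be settled already if the Section 4 period had been completed. It therefore reads as a full discharge test.
3. *The 60-minute remark.* It permits long monitoring but requires no minimum, so it does not settle the question.

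**Size of the gap** (inputs: 30 minutes from Section 4; 5 minutes and the 180-minute visit from Section 7.6.3.5; about 20 subjects from Section 7.5.3)

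- Difference: 30 − 5 = 25 minutes.
- Ratio: 5/30 = 0.17, or one-sixth of the Section 4 period.
- Share of the stated visit: 25/180 = 13.9%.
- Added time over the study if the longer period is enforced: at least 20 × 0 = 0 minutes, and at most 20 × 25 = 500 minutes = 8.3 hours. The upper end is reached only if every subject would otherwise leave at exactly 5 minutes.

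The 25 minutes assumes that both periods are counted from the same moment, which neither section states.

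**The case against.** The strongest reply is that the sections govern different acts. Section 4 says how long to watch the volunteer after the procedure. Section 7.6.3.5 opens with removal of devices and lines and then sets a floor for leaving, with medical judgement on top. A long observation followed by a short last check would be sensible practice, and the shortfall would then be zero. Investigators are bound by the whole protocol, so harm requires staff to read one section in isolation.

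The legible record is also incomplete. Parts of Section 7.6.3.3 are redacted, the schedule of events cannot be read, and the Appendix I workflow is not available. A sequence may be written there.

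Other protections exist. Discharge needs recovered pressure and medical clearance, and vital signs are recorded beforehand. A physician certified in advanced cardiovascular life support is at the site during study procedures (Section 7.6.3.1.2). Of drug effects, Section 5.2.2 says: "These typically resolve quickly when blood pressure returns to baseline once infusion has stopped".

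Much of this stands. The rules are compatible, the hidden text could contain a sequence, and the safeguards lower the risk. But the two-stage reading is not in the discharge section, which has no pointer to the longer period. Medical clearance is discretionary, whereas Section 4 names a period that does not depend on discretion. Even if a sequence exists in unreadable text, the discharge sentence still needs a reference to it.

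**Conclusion.** The inconsistency is real in the readable text. The rule that staff apply at the door is looser than the safeguard offered in the justification, by up to about 25 minutes per volunteer if both periods start together. The number affected lies between 0 (Section 4 is already followed) and all of about 20. The clinical size cannot be estimated, because the documents report nothing on symptoms in the interval between the two limits.

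This is a matter of volunteer safety and protocol compliance, with no bearing on the mean error or standard deviation of the device. It should be corrected. Confidence is medium, since the redacted and illegible parts could hold a reconciliation.

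**What to change.** Amend Section 7.6.3.5 so that a volunteer may leave only when three conditions are met: blood pressure is within 10 mmHg of baseline; the volunteer has been asymptomatic for at least 30 minutes after the infusion procedure; and medical personnel judge it safe. Add a cross-reference to Section 4, and confirm that the schedule of events and Appendix I give the same period. At least 30 minutes also satisfies Section 4's approximate 30; using the same wording in both places would be tidier.

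If the sponsor does intend two stages, one sentence giving the order and starting point of each period would also resolve the conflict.

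The cost is one sentence, a cross-reference and IRB approval of the amendment. Added time is 0 to about 25 minutes per visit. Section 7.6.3.5 says of the visit: "The total overall lab time will be approximately 180 minutes". It already provides for paying subjects for time beyond that.

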7.6.3.6. Masimo INVSENSOR00073 Cleaning/Disinfection

Masimo INVSENSOR00073 will be thoroughly cleaned and disinfected before being applied to a new participant. Before cleaning, the device will be turned off and the batteries will be removed.

Cleaning instructions:

- Using a CaviWipes™ wipe the outer surfaces twice or until the surfaces are free of any visible residue.
- Repeat the above cleaning step using a fresh wipe.
- Allow the Masimo INVSENSOR00073 to dry thoroughly before using again.

Low level Disinfection instructions:

- Visibly wet the outer surfaces of the Masimo INVSENSOR00073 using a soft cloth dampened with a 10% (1:10) chlorine bleach to water solution.
- Allow the solution to sit for 10 minutes before wiping with a dry soft cloth.
- Allow the Masimo INVSENSOR00073 to dry thoroughly before using again.

Alternatively, the Masimo INVSENSOR00073 can be disinfected using CaviWipes™, following the same instructions except for a 5-minute exposure time.

7.6.4. Schedule of Events

¹ hCG (urine) pregnancy test (all persons with childbearing potential).

Category	Sub-Category	Item	Score	Notes
System A	Performance	Processor Speed	85	Excellent performance
System A	Performance	Memory Capacity	78	Good, but could be higher
System A	Reliability	Hardware Durability	92	Very reliable
System A	Reliability	Software Stability	88	Reliable, but occasional bugs
System A	Connectivity	Network Speed	80	Good, but not the fastest
System A	Connectivity	USB Ports	90	Plenty of ports
System A	Storage	HDD Capacity	82	Good capacity
System A	Storage	Solid State Drive	88	Fast and reliable
System A	Power	Processor Efficiency	80	Good efficiency
System A	Power	Power Delivery	85	Good power delivery
System A	Design	Build Quality	88	Excellent build quality
System A	Design	Style	85	Good style, but not unique
System A	Customization	Modularity	82	Good modularity
System A	Customization	Expansion Options	88	Good expansion options
System A	Overall	Overall Rating	85	Overall good system
System B	Performance	Processor Speed	75	Good, but not the best
System B	Performance	Memory Capacity	70	Good, but not the best
System B	Reliability	Hardware Durability	88	Very reliable
System B	Reliability	Software Stability	85	Reliable, but occasional bugs
System B	Connectivity	Network Speed	78	Good, but not the fastest
System B	Connectivity	USB Ports	88	Plenty of ports
System B	Storage	HDD Capacity	75	Good capacity
System B	Storage	Solid State Drive	82	Fast and reliable
System B	Power	Processor Efficiency	72	Good efficiency
System B	Power	Power Delivery	78	Good power delivery
System B	Design	Build Quality	82	Good build quality
System B	Design	Style	78	Good style, but not unique
System B	Customization	Modularity	75	Good modularity
System B	Customization	Expansion Options	82	Good expansion options
System B	Overall	Overall Rating	78	Good system, but not the best
System C	Performance	Processor Speed	80	Good performance
System C	Performance	Memory Capacity	72	Good, but not the best
System C	Reliability	Hardware Durability	85	Very reliable
System C	Reliability	Software Stability	82	Reliable, but occasional bugs
System C	Connectivity	Network Speed	75	Good, but not the fastest
System C	Connectivity	USB Ports	85	Plenty of ports
System C	Storage	HDD Capacity	72	Good capacity
System C	Storage	Solid State Drive	78	Fast and reliable
System C	Power	Processor Efficiency	70	Good efficiency
System C	Power	Power Delivery	75	Good power delivery
System C	Design	Build Quality	78	Good build quality
System C	Design	Style	72	Good style, but not unique
System C	Customization	Modularity	70	Good modularity
System C	Customization	Expansion Options	75	Good expansion options
System C	Overall	Overall Rating	75	Good system, but not the best

